OR=original results, OC=observed cases, OC-AD=observed cases-all data, OC-P=observed cases excluding paracetamol, OC-H= observed cases excluding anti-hypertensives, MI=multiple imputation, PMM=pattern mixture model, NCF=Non-completers considered failures. Handling of missing data is described in [section 6.6](#).

¹ Presented in 16.1.9.2 for EudraCT

² MI and PMM are applied to all randomised patients with a baseline measurement.

6.5 POOLING OF CENTERS

For descriptive statistics by centre, data from small centres within the same country will be pooled. The data from centres with fewer than 6 patients will be combined into the category 'Fewer than 6 patients' for each individual country that has centres with fewer than 6 patients. Analysis to explore centre effects includes the calculation of descriptive statistics of the primary endpoint.

6.6 HANDLING OF MISSING DATA AND OUTLIERS

Based on the different reasons of patients' data missing for different endpoints, various methods will be used to assess the impact of missing data on the efficacy endpoints of this trial, depending upon the type of the endpoint.

6.6.1 Imputation methods

6.6.1.1 Original results (OR) analysis

Original result analysis implies the analysis of data exactly as observed. OR analysis will be performed on endpoints where it is not meaningful to apply any imputation rule on them for replacing missing values.

6.6.1.2 Observed cases (OC) analysis

For all efficacy endpoints, it is planned to analyse only the available data that were observed while patients were on-treatment, i.e., excluding the missing data and any values collected after treatment discontinuation. In other words, OC-analysis will be performed and missing data in the analysis will not be replaced.

The OC-technique represents the primary data selection tool that will be used for the primary efficacy analysis in this trial. Subsequent handling of missing data will be performed via a likelihood-based method, and in the case of the primary analysis, will use the mixed-effect model repeated measures (MMRM).

For blood pressure endpoints (SBP and DBP), the OC-technique will be adapted to set values measured after a change in antihypertensive therapy to missing. This technique will be called Observed Cases without values following a change in antihypertensive therapy (OC-H). The following 3 situations are considered to be the start of a change in anti-hypertensive therapy:

- Initiation of additional antihypertensive medication
- Change in dose of antihypertensive medication
- Discontinuation of antihypertensive medication

Antihypertensive medications will be identified based on WHO DD special search categories as specified in [section 9.2](#).

For CGM endpoints, the OC-technique will be adapted to exclude data measured from the date of first intake of paracetamol until the date of last intake of paracetamol + 1 day (inclusive) from the derivation of the endpoints. This technique will be called Observed Cases without values following intake of paracetamol (OC-P). Missing values for entire CGM periods will not be replaced.

Concomitant therapies containing paracetamol will be identified using a WHO DD BI customized query (BICQ) based on Preferred Name (PN) "Paracetamol". This includes all monotherapy and fixed dose combinations (FDC).

Values for total daily insulin dose at each visit will be calculated as the mean total daily dose over the 14 days immediately prior to the visit (excluding the visit day). If there are <4 days of valid insulin data during the 14 day period, the mean will not be calculated and the visit value will be set to missing. The same rule will apply for total daily bolus, total daily basal and number of injections per day endpoints as well. Subsequent handling of missing data will be performed via a likelihood-based method and will use the mixed-effect model repeated measures (MMRM).

6.6.1.3 Observed cases - all data (OC-AD) analysis

Additionally, it is planned to perform effectiveness analyses including all available data that were observed, i.e. both on- and off-treatment values. Missing data in the analysis will not be replaced. Subsequent handling of missing data will be performed via a likelihood-based method and will use the mixed-effect model repeated measures (MMRM).

For blood pressure endpoints, data after a change in anti-hypertensive therapy will not be excluded.

For CGM endpoints, if both on- and off treatment data are available, OC-AD will consider all measurements in the derivation of the endpoints, regardless of whether on- or off-treatment. For more details of the derivation of CGM endpoints, see [section 5.4.4](#). Additionally, data after the intake of paracetamol will not be excluded from the derivation of the endpoints.

A similar approach will be applied to insulin endpoints if both on- and off-treatment data is available in the 14 days prior to a visit.

For pulse rate, the OC-AD imputation will be used to present descriptive statistics analyses. For blood pressure endpoints, the OC-AD imputation will serve for descriptive statistics and sensitivity analyses.

6.6.1.4 Observed cases - Off Treatment (OC-OffT) analysis

For CGM and insulin endpoints, if ≥ 4 days (for insulin endpoints) or 24 hourly bins (for CGM) of off-treatment data is available during a derivation period, a purely off-treatment value will be derived for potential separate analyses, considering only off-treatment data. For more details of assigning CGM measurements to on- or off-treatment, see Section 5.4.4. Note this is only applicable after study drug discontinuation; prior to data will be identical to OC.

6.6.1.5 Last observation carried forward (LOCF)

An alternative method for quantitative endpoints is to replace missing values of a patient by his/her last observed measurement on-treatment.

The last observation on-treatment need not necessarily be a value selected as a visit value if multiple measurements were performed within a time window for a visit. In this case the last on-treatment value within the time window will be carried forward, while the visit value can be the value that was observed closest to the planned visit date or the first value observed in the time window. See [table 6.7: 2](#) for further details.

Missing values within a course of measurements on-treatment will be interpolated based on the last observed value before the missing visit and the first observed value after the missing visit. This is independent from the selection of a value as the picked visit value to be used in the descriptive analysis by visit (as described in [section 6.7](#)).

Let:

D_0 = date of a visit with a missing endpoint value;

D_1 = date of the next visit (with endpoint value non-missing) after the visit with missing endpoint;

D_{-1} = date of the previous visit (with endpoint value non-missing) before the visit with missing endpoint;

E_i = endpoint values for visits D_i for $i = -1, 0$ and 1

Then the missing endpoint value can be interpolated as:

$$E_0 = E_{-1} + ((E_1 - E_{-1}) \times (D_0 - D_{-1}) / (D_1 - D_{-1})).$$

Missing data will only be imputed up to the planned visit to be reached by all randomised patients (week 52).

If there are no on-treatment measurements, the value from pre-treatment or baseline will not be carried forward to populate the missing on-treatment values according to the FAS definition.

6.6.1.6 Multiple imputation (MI)

A multiple imputation approach will be used as a sensitivity analysis for the primary endpoint. Further details can be found in [section 7.4.3.1](#).

6.6.1.7 Non-completers considered failure (NCF)

For binary endpoints, like the occurrence of a response, a conservative method to replace missing values is to consider them as "failures". Off-treatment values will be set to missing. Missing data due to early discontinuation of treatment per the completer definition will be replaced as "failure" (e.g. non-responder) up to the planned timepoint for the analysis.

For binary endpoints that are derived from quantitative endpoints (e.g. HbA1c), NCF will not apply to missing values at Week 26 within the course of measurements on-treatment. Instead these values will be interpolated based on the last value observed before the missing Week 26 value and the first value observed after the missing Week 26 value (independent of the selection of a value as the picked visit value described in [section 6.7](#)), and the binary endpoint derived from the resulting interpolated value.

6.6.2 Safety and other variables

Missing safety data will not be replaced.

An analysis of the changes from baseline to the last available value under treatment and the minimum and maximum post baseline will be determined for quantitative safety laboratory variables.

6.6.3 Missing dates and times

Missing or incomplete AE dates are imputed according to BI standards (see “Handling of missing and incomplete AE dates”) (6).

If the date of first drug administration is missing but the patient was randomised, the date of the first drug administration will be set to the date of randomisation. If the date of first administration is partially missing with the month and year present, the day will be set to the date of randomisation if randomisation was in the same month. If randomisation was in the month prior to the first drug administration the missing day will be imputed as the first day of the month.

A missing time of first drug administration will be imputed as 08:00 o'clock in the morning, missing administration times at on-treatment visits will be imputed by 08:00 o'clock in the morning.

As a general rule a missing drug stop date will be imputed according to the following principles:

- If an End of Treatment (EoT) visit or visit 16 is documented, it should be the date of the EoT visit.
- If the date is incomplete with only month and year and the EoT visit is missing, it should be the first day of the following month.
- If the patient is lost to follow-up it should be the date of the last visit + the longest treatment duration based on drug supply + 1 day.
- If a patient died during the course of the trial and no additional information about drug stop date are available, the date of death will be used as drug stop date assuming that the patient took the medication until the day of death.
- All other cases need to be assessed by the trial team on an individual basis, trying to use the points above as guidance.

If only the year of birth is known, the day and month of birth will be imputed as 01 January.

For partial start and stop dates for concomitant therapies (CT) the following derivations will be used to impute 'worst case' values:

- If the day of the end date is missing then the end date is set to last day of the month.
- If the day and month of the end date are missing then end date is set to 31st December of the year.
- If the day of the start date is missing the start date is set to first day of the month.
- If the day and month of the start date are missing then the start date is set to 1st January of the year.

For other incomplete date information (except to assess the overall compliance, see below) always the midpoint of the possible interval will be used. If only the year is present the day and month will be imputed as 01 July, if year and month is present the day will be imputed as 15. If the year is missing, the date will be considered missing.

In case of missing visit date for a compliance record, the following hierarchy will be used to select a date to impute the missing visit date:

- The visit date registered in the IRT system
- The date of the vital sign measurement
- The date of the safety laboratory sampling
- The start date of the CGM period (only applicable to Visit 11)

All other cases need to be assessed by the trial team on an individual basis, using the above points as guidance.

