- The patient e-diary will be checked after which it should be removed from the patient, together with all other study-related devices and equipment, once Visit 17 is complete
- 6.2.3.4 Follow-up visit (Visit 17) early discontinuations (eEOT) and withdrawals

For patients who discontinue treatment prematurely prior to completion of 52 weeks the following should be performed whenever possible once an eEOT Visit has been completed (see Section 6.2.3.2):

- 3 weeks after the date of the eEOT Visit, patients should complete Visit 17. Visit 17 should be done with the patient in a fasted state (i.e. no food or drink except water for 10 hours), and all assessments indicated in the Flow Chart for Visit 17 should be performed
- Thereafter, patients should be followed up according to the visit schedule (e.g. a patient who discontinued study medication a week after Visit 12 (Week 26) i.e. at Week 27 would next be followed up for Visit 13 (Week 34) after having completed an eEOT visit as soon as possible after Week 27, and a Visit 17 at Week 30
- The Investigator may negotiate a revised visit schedule should the patient be unwilling or unable to adhere to the regular schedule according to the Flow Chart. These follow-up visits may occur by telephone or in the clinic but Visit 12 (Week 26) and Visit 16 (Week 52) must be performed as a clinic visit in order to complete all scheduled assessments
- When being followed up according to the visit schedule, only assessments relating to the primary and key secondary endpoints and general safety have to be completed (i.e. weight, vital signs, physical examination, ECG, safety laboratory, pregnancy test, HbA1c, e-diary completion, CGM periods (in patients from participating countries) and the

Page 74 of 144

Proprietary confidential information © 2017 Boehringer Ingelheim International GmbH or one or more of its affiliated companies

collection of AEs and changes in concomitant therapy). All other assessments

• Visit 16 EOT at 52 weeks will be the last visit for these patients, since Visit 17 will already have been completed 3 weeks after the eEOT Visit as explained above. At Visit 16 EOT therefore, the patient e-diary will be checked after which it should be removed from the patient, together with all other study-related devices and equipment, once the visit is complete

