7.4 PRIMARY ENDPOINT

7.4.1 Primary analysis

The primary endpoint in this trial is the change from baseline in HbA_{1c} (%) at 26 weeks. Efficacy and effectiveness will be tested in a hierarchical manner.

The primary efficacy analysis will be performed on the FAS (OC). Patients will be assigned to the treatment they were randomised to. Only on-treatment HbA_{1c} values will be included in the primary analysis. Only data up to the Week 26 timepoint will be included. All randomised treatment groups will be included in the same analysis.

Mean changes from baseline in HbA_{1c} after 26 weeks will be analysed using a restricted maximum likelihood-based repeated measures approach (MMRM analysis). Analyses will include the fixed categorical effects of treatment, pre-existing insulin therapy, week and treatment by week interaction, as well as the continuous, fixed covariates of baseline HbA_{1c}, baseline eGFR and baseline HbA_{1c} by week interaction. Patient will be included as random effect. An unstructured (co)variance structure will be used to model the within patient measurements.

If this analysis fails to converge, the following covariance structures will be tested: first-order ante-dependence (ANTE(1)), heterogeneous Toeplitz (TOEPH), Toeplitz (TOEP) and first-order autoregressive (AR(1)). The (co)variance structure converging to the best fit, as determined by Akaike's information criterion, will be used as the primary analysis.

The Kenward-Roger approximation will be used to estimate denominator degrees of freedom. Significance tests will be based on least-squares means using a two-sided $\alpha = 0.025$ (two-sided 97.5% confidence intervals). The residuals are assumed to have a multivariate normal distribution with zero means and covariance matrix as specified above. The primary treatment comparisons will be the contrasts between active treatments and placebo at Week 26.

The statistical model will be:

HbA_{1c} change from baseline = overall mean + continuous baseline HbA_{1c} + pre-existing insulin therapy + continuous baseline eGFR + treatment + week + baseline HbA_{1c} by week interaction + treatment by week interaction + random error

If the null hypothesis is successfully rejected for the efficacy analysis, then an effectiveness analysis will be performed on the mITT (OC-AD), including both on- and off-treatment data. The model will be the same as the model for the efficacy analysis described above.

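### The SAP's stop-date rules can give an early discontinuer a Week 52 stop, or a stop outside the recorded month, so off-drug values can count as on-treatment

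*SAP*

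**What the plan says.** SAP 6.6.3 gives ordered principles for a missing drug stop date. The first is "If an End of Treatment (EoT) visit or visit 16 is documented, it should be the date of the EoT visit". The second covers a date that is "incomplete with only month and year and the EoT visit is missing, it should be the first day of the following month". Bullets on loss to follow-up and death come next, and the list ends: "All other cases need to be assessed by the trial team on an individual basis, trying to use the points above as guidance".

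The same section handles other partial dates differently. For concomitant therapy, "If the day of the end date is missing then the end date is set to last day of the month". For the residual class of incomplete dates, "always the midpoint of the possible interval will be used", so "if year and month is present the day will be imputed as 15".

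Protocol 6.2.3.4 keeps patients who stop drug early in follow-up, requires clinic visits at Weeks 26 and 52, and states that "Visit 16 EOT at 52 weeks will be the last visit for these patients". Protocol 6.2.3.2 asks for an early end-of-treatment (eEOT) visit and has patients who stop drug but stay in follow-up registered in IRT as withdrawn from treatment.

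The stop date then decides what counts as on-treatment. SAP 6.1 and Table 6.7: 1 extend the on-treatment period by 7 days for HbA1c, 1 day for weight, blood pressure and hypoglycaemia, and 0 days for insulin dose. In SAP 7.4.1 only on-treatment HbA1c "values will be included in the primary analysis. Only data up to the Week 26 timepoint will be included".

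**The concern.** The first principle treats a documented Visit 16 as evidence of when drug ended. That is true for completers, who take their last dose at that visit (Protocol 6.2.3.1). It is not true for early discontinuers who attend Week 52 off drug, and the rule does not separate the two groups. The second principle picks a day that cannot be right if the recorded month is right.

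Both errors run late, so what is at stake is off-drug data being labelled on-treatment: HbA1c in the primary efficacy test, and weight, blood pressure, insulin dose and hypoglycaemia time in the confirmatory key secondary tests. The same date also feeds FAS membership, the Week 26 cut-off, adverse event assignment and exposure.

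**Working it through.** **1. The plan's own figures.** Protocol 7.7 uses a difference of 0.3, SD 0.9, two-sided alpha 0.025 and 90% power. The two-sample t-test (noncentral t) gives 225 per arm, with power 90.05%. Allowing 6% outside the FAS: 225 / 0.94 = 239.4, so 240 per arm and 720 in total. This agrees with the protocol. The HbA1c window ends in SAP Table 6.7: 2 also follow from the midpoint rule: (28 + 84)/2 = 56, (84 + 126)/2 = 105, (126 + 182)/2 = 154, (182 + 301)/2 = 241.5, taken as 241.

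**2. Visit 16 route.** Take a patient with no eEOT visit on record, a missing stop date and an attended Visit 16 on Day 364. The imputed stop is Day 364. A planned HbA1c on day d is wrongly labelled on-treatment if d > true stop + 7.

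| True stop (day) | Planned HbA1c days mislabelled, to Week 26 | Days off drug at Day 182 |
|---|---|---|
| 60 | 84, 126, 182 | 122 |
| 70 (Week 10) | 84, 126, 182 | 112 |
| 112 | 126, 182 | 70 |
| 150 | 182 | 32 |
| 175 | none | 7 |

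A sample on Day 182 is mislabelled for any true stop before Day 175, since 182 − 7 = 175. The patient also falls under the still-on-treatment branch of the Week 26 cut-off in SAP 6.1. For a Week 10 stop this adds about 26 − 10 = 16 weeks of off-drug time to the hypoglycaemia time at risk.

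**3. Month-only route.** In a 31-day month the true day is 1 to 31 and the imputed day is in effect day 32. The error is 32 − 31 = 1 to 32 − 1 = 31 days late, and never early. Adding the 7 days for HbA1c, a sample up to 31 + 7 = 38 days after the last dose counts as on-treatment (35 to 37 in shorter months).

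Example: true stop 3 June, recorded as June, Week 26 sample on 25 June. The sample is 25 − 3 = 22 days off drug. By the true date the on-treatment period ends on 10 June; by the imputed date (1 July) it ends on 8 July.

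**4. Alternatives for a 31-day month.**

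| Rule | Error (days) | Mean error if all days are equally likely |
|---|---|---|
| First day of next month | +1 to +31 | +16 |
| Last day of recorded month | 0 to +30 | +15 |
| Day 15 | −16 to +14 | −1 |

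Stepping out of the month adds one day. The rest of the lateness belongs to any latest-date convention.

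**5. Illustrative size.** The documents give no count, so assume that a fraction f of an active arm is mislabelled with no remaining effect at Week 26, and that placebo is unaffected. The effect becomes 0.3 × (1 − f). Power is for 225 per arm, SD 0.9 and alpha 0.025.

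| f | Effect | Power |
|---|---|---|
| 0 | 0.300 | 90.0% |
| 1% | 0.297 | 89.4% |
| 2% | 0.294 | 88.8% |
| 5% | 0.285 | 86.6% |
| 10% | 0.270 | 82.4% |

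One per cent of 225 is about two patients.

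**The case against.** The natural reading of the first principle is the eEOT visit for early stoppers and Visit 16 for completers. Footnote A of SAP Table 6.7: 2 says that an eEOT visit has to take place after premature discontinuation. The Week 52 route therefore needs a patient followed to Week 52 off drug with neither an eEOT visit nor a stop date, or a reading that prefers Visit 16 when both visits exist. The rules are also introduced as general principles, so an evident misfit could be reviewed. This makes the case rare, but it does not close it: the protocol says only that the eEOT visit should be done, imputation rules exist for incomplete records, and individual review is reserved for cases that the bullets do not cover.

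The month-only rule can be defended as a latest-date convention. A late stop date avoids dropping adverse events that were truly on treatment, and concomitant-therapy end dates are handled in the same spirit. That stands. Only the step outside the recorded month cannot be defended, and it is worth one day.

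A reader might infer several stronger points that the documents do not support:

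- That off-drug values do enter the primary analysis. They can, but only for patients with a missing or partial stop date, and no number is given.
- That a recorded stop month would be overridden by a Week 52 date. This depends on what the second principle means by the EoT visit. If it means the eEOT visit for an early stopper, the month rule applies instead.
- That day 15 should replace the rule. The SAP applies day 15 only to dates without a rule of their own. It can fall 16 days before the true last dose, which would move real on-drug values and events off-treatment.

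**Conclusion.** The point holds as a defect of wording with small expected consequences. As written, SAP 6.6.3 permits a Week 52 stop date for a patient who stopped early, and it always places a month-only stop outside the recorded month.

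The number of patients affected is unknown and probably very small. At 1% to 2% of an active arm, and on the pessimistic assumption of no remaining effect, power falls by about 0.6 to 1.3 percentage points. For month-only dates that assumption is harsh, because HbA1c reflects roughly the preceding 12 weeks (Protocol 3.2).

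A reader might take this for a threat to type I error. The documents do not support that: off-drug values in the active arms would usually pull the on-treatment HbA1c difference toward zero. The direction for hypoglycaemia is not established. Data inclusion in the effectiveness analysis (mITT, OC-AD) hardly depends on the stop date, because on- and off-treatment values both count there; only the preference for a value on the last day of drug is touched. The key secondary tests are reached only if that analysis also succeeds, although their own confirmatory analyses use on-treatment data.

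**What to change.** Amend SAP 6.6.3 in three places:

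- Use Visit 16 as the stop date only for patients not registered in IRT as withdrawn from treatment.
- For registered patients use the eEOT date. If there is none, use a date no later than the IRT withdrawal registration and no earlier than the last recorded dose.
- For a stop known only by month and year, keep the imputed date within that month, for example its last day as for concomitant-therapy end dates, and no later than the eEOT visit or the IRT withdrawal date.

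The cost is a few sentences and a little programming. Protocol 6.2.3.2 already requires the IRT registration, and SAP 6.6.3 already uses IRT dates for missing compliance visit dates. Two limits remain. The IRT date bounds the last dose and does not measure it. A last-day rule can still be up to 30 days late where no earlier bound exists.
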